7.4.1.1.5 Important Medical Events and events of special interest - amended

The Important Medical Events (IME) list is developed and published by European Medicines Evaluation Agency (EMA) (<http://eudravigilance.ema.europa.eu/human/textforIME.asp>). All AEs reported in this study will be reviewed against the most current IME list periodically, and any events that are contained on the IME list will be specifically reviewed and the Investigator will be asked to review and confirm whether or not the event meets the criteria for seriousness in his/her opinion. In addition, the following events of special interest will be closely reviewed by the sponsor's study medical expert:

- Perforations of the uterus, cervix or fallopian tubes.³⁷
- Upper genital tract infections (for example: endometritis, salpingo-oophoritis, salpingitis).
- Expulsion or migration of Essure inserts.
- Potential allergy/hypersensitivity to Essure inserts (for example: itch [pruritus], rash, hives [urticaria], facial edema, angioedema, allergy to metals).³⁷

7.4.1.2 Classifications for adverse event assessment

All AEs will be assessed and documented by the investigator according to the categories detailed below.

7.4.1.2.1 Seriousness

For each AE, the seriousness must be determined according to the criteria given in Section 7.4.1.1.

7.4.1.2.2 Severity

The severity of an AE is classified according to the following categories:

- Mild: asymptomatic or mild symptoms; clinical or diagnostic observations only; intervention not indicated.
- Moderate: minimal, local, or noninvasive intervention indicated; limiting age appropriate instrumental activities of daily living (ADL).
- Severe: or medically significant but not immediately life threatening – hospitalization or prolongation of hospitalization indicated, disabling; limiting self-care ADL.

³⁷ Added per Amendment 6.

7.4.1.2.3 Causal relationship

The assessment of the causal relationship between an AE and the administration of treatment is the investigator's responsibility, and is a clinical decision based on all available information at the time of the completion of the CRF. The assessment is based on the question of whether there was a "reasonable causal relationship" to the study treatment in question.

The following information must be entered on the CRF for all AEs and SAEs:

- Relation to the Essure device
- Relation to the NovaSure device
- Relation to the NovaSure procedure
- Relation to a pre-existing condition (additional description required)

Possible choices for causality include:

- Not related
- Unlikely to be related
- Possibly related
- Probably related
- Definitely related

Important factors to be considered in assessing the relationship of the AE to the device or procedure include:

- The temporal sequence from the Essure placement procedure: The event should occur after the procedure.
- Underlying, concomitant, intercurrent diseases:
Each event should be evaluated in the context of the natural history and course of the Essure procedure and any other medical conditions the subject may have.
- Concomitant medication or procedures:
Any drugs the subject is taking or additional procedures the subject receives should be examined to determine whether any of them may be suspected to cause the event in question.

7.4.1.2.4 Outcome

The outcome of the AE is to be documented as follows:

- Recovered without treatment
- Recovered with treatment
- Not recovered with permanent impairment
- Death
- Undetermined, describe:

7.4.1.3 Assessments and documentation of adverse events³⁸ - amended

Investigators must collect all AEs for each subject from the time of signing of the informed consent through the end of subject study participation, whether or not deemed related to the investigational device or procedure. All AE data will be recorded on the CRFs as well as documented in the subject's medical record and study source documents.³⁹

All SAEs and SADEs will be followed until the event has subsided or, in case of permanent impairment, until the event stabilizes and the overall clinical outcome has been ascertained.

Investigator must determine whether adverse event meets the definition of a serious adverse event; if so, it must be reported as required by Section 7.4.1.1.

Any SAE or incident will be reviewed and processed by the sponsor according to all applicable regulations.

Investigators must document all device failures, malfunctions and use errors, including the assessment of whether the event is considered an incident (ADE) using the Device Malfunction and Failure CRF.

Because an approved device will be used for the placement procedure, any device malfunctions will be reported to the sponsor's Product Surveillance department. Device malfunctions will not be analyzed as part of this study as the placement procedure and devices are not being evaluated.

7.4.1.4 Reporting of serious adverse events - amended

The definition of serious adverse events (SAEs) is given in Section 7.4.1.1. These include device deficiencies that may have led to a SAE if a) suitable action had not been taken or b) intervention had not been made or c) if circumstances had been less fortunate. These are handled under the sponsor's SAE reporting system.

Investigator's notification of the sponsor

All investigators will be thoroughly instructed and trained on all relevant aspects of the investigator's reporting obligations for SAEs. This information, including all relevant contact details, is summarized in the investigator site file. This information will be updated as needed.

All SAEs and SADEs occurring during the observation period defined in Section 7.4.1.3 must immediately (within 24 hours of the investigator's awareness) be reported to the sponsor.⁴⁰ An SAE form must also be completed within 24 hours of the investigator awareness and forwarded to the sponsor's designated recipient.

Each SAE and incident must be followed up until resolution or stabilization by submission of updated reports to the designated recipient. Any SAE or incident occurring after the protocol-defined observation period will be processed by the sponsor according to all applicable regulations.

³⁸ Section was updated per Amendment 6.

³⁹ Per Amendment 5

⁴⁰ Sentence modified per Amendment 6.

In addition, device failures, malfunctions or incidents must be reported to Sponsor within 24 hours via fax or email.

Ectopic pregnancies and spontaneous abortions will always be considered as SAEs and reported as such to the Sponsor

Notification of the independent ethics committee (IEC)s / institutional review board (IRB)s

Notification of the IECs / IRBs about all relevant events (e.g. SAEs, incidents, UADEs, device failures, device malfunctions) will be performed by the investigator according to all applicable regulations.

Notification of the authorities

The processing and reporting of all relevant events (e.g. SAEs, incidents, UADEs, device failures, device malfunctions) to the authorities will be done by the sponsor according to all applicable regulations.

Because this is a PAS, the Essure System is subject to Medical Device Reporting (MDR) regulations. The sponsor will review all serious adverse events and unanticipated adverse device effects and determine their reportability to FDA according to 21 Code of Federal Regulations 803 "*Medical Device Reporting*" Reporting MDRs to FDA is required when the sponsor becomes aware of information that reasonably suggests that a marketed device has or may have caused or contributed to a death, serious injury or long-term pain necessitating surgical intervention, or has malfunctioned, and that the device or a similar device marketed by the manufacturer would be likely cause or contribute to a death or serious injury if the malfunction were to recur. In the event information is received that the NovaSure System may have caused or may have contributed to a death or serious injury, the sponsor will notify the complaint handling function of the manufacturer of the device (Hologic, Inc.).

Sponsor's notification of the investigational site

The sponsor will inform all investigational sites about reported relevant events (e.g. SAEs incidents, UADEs, device failures, device malfunctions) according to all applicable regulations.

If the adverse event is the result of an unanticipated adverse device effect, the investigator must report it to the sponsor within 3 working days after the investigator becomes aware of the event.⁴¹ The investigator will send to the sponsor all pertinent paperwork (discharge summaries, office notes, etc.) within 5 working days.

Reports relating to the subject's subsequent medical course must be submitted to the sponsor until the event has subsided or, in case of permanent impairment, until the event stabilizes and the overall clinical outcome has been ascertained. The investigator must report it to the Ethics Committee / IRB within the required time frame.

⁴¹ Wording modified per Amendment 6.

7.4.1.5 Expected adverse events

For this medical device study, the applicable reference document is the most current version of the IFU.

The expectedness of AEs will be determined by the sponsor according to the applicable reference document and according to all local regulations.

7.4.2 Device removal⁴² – *new section*

Each time a removal procedure is performed, additional information will be collected about the circumstances surrounding the removal (reason for removal, procedure details, any energy sources used, vasoconstrictive agent used, imaging to assist with confirming the location of the insert, and the location and status of the device removed).

7.4.3 Pregnancies⁴³

If a subject becomes pregnant at any time during the study, the pregnancy will be counted as an Essure device failure following a NovaSure ablation. Subject will also be counseled that she can no longer rely on Essure for contraception.

The Investigator must report to the Sponsor any pregnancy occurring in a study subject during the subject's participation in this study. The report should be submitted within the same timelines as an SAE, although a pregnancy per se is not considered an SAE.

For a study subject, the outcome of the pregnancy should be followed up carefully, and any outcome of the mother or the child should be reported. For all reports, the forms provided are to be used.

7.5 Other procedures and variables⁴³

Not applicable.

7.6 Appropriateness of procedures / measurements⁴³

Not applicable.

8. Statistical methods and determination of sample size

8.1 General considerations

The statistical analysis plan will be finalized and signed off before data release for analysis.⁴⁴

Baseline NovaSure EA and follow-up data will be summarized using the appropriate statistical method. Continuous variables will be summarized using means, standard deviations, medians and ranges. Categorical data will be summarized using frequency rates (e.g., count/sample size).

⁴² Section added per Amendment 6.

⁴³ Per Amendment 4

⁴⁴ Per Amendment 4

8.2 Analysis sets⁴⁵

Primary effectiveness cohort

All subjects who meet study entry criteria, sign a study-specific ICF, and undergo insertion of the NovaSure device transcervically.

Primary safety cohort

All subjects in whom a NovaSure procedure is attempted.

8.3 Variables⁴⁶

- **Primary:** Occurrence of confirmed pregnancy at 1 year and 3 years among subjects relying on Essure micro-inserts for permanent birth control when NovaSure is performed following a successful Essure Confirmation Test.
- **Secondary:** Adverse event data

8.4 Statistical and analytical plans

8.4.1 Primary Endpoint

The primary effectiveness endpoint of this study is the 1-year and 3-year pregnancy rates. The rates will be calculated as done in prior Essure studies, as described below.

Each woman-month of follow-up represents a “Bernoulli trial” of the Essure device. A woman contributes as many women-months as her participation in the post-approval study. Upon observing f failures in w women-months, the posterior distribution of the monthly failure rate, r , is calculated as:

$$r = \text{beta}(a+f, b+w-f)$$

where a and $b = 0.5$, representing a non-informative prior distribution. The upper Bayesian credible interval of r is easily calculated from the inverse beta function. A 1-year failure rate can be calculated as:

$$1\text{-year rate} = 1 - (1-r)^{12}$$

The 1-year rate will be calculated when all participating women have reached at least 1 year of follow-up.

As an additional related calculation, we will determine the 3-year failure as:

$$3\text{-year rate} = 1 - (1-r)^{36}$$

For example, if there are 0 failures in $200 \times 12 = 2,400$ women-months, the posterior distribution of the monthly failure rate is $\text{beta}(0.5, 0.5 + 2400)$. The upper Bayesian credible interval is (in Excel) $\text{betainv}(.975, 0.5, 0.5 + 2400) = 0.00105$. The upper 95% credible

⁴⁵ New section from sponsor template per Amendment 4

⁴⁶ New section from sponsor template; populated with text from previous version per Amendment 4

interval for the 1-year rate is $1-(1-0.00105)^{12} = 0.0125$ or 1.25%⁴⁷. This value meets the pre-determined study success threshold of 2.1%.

8.4.2 Secondary Endpoint

The secondary endpoint in the PAS is the incidence of adverse events when NovaSure EA is performed in the presence of Essure micro-inserts. There is no specific study hypothesis.

8.5 Planned interim analyses

For the first two years of the PAS, an interim PAS status report will be submitted every 6 months from the date of the pre-market approval (PMA) letter or other negotiated starting date (i.e., PAS initiation). Ongoing interim PAS status reports will be submitted annually, thereafter, until the final PAS report is written after the termination or completion of the PAS. The ongoing interim reports and final PAS report will include information related to PAS methodology and results/endpoints.

8.6 Determination of sample size

The primary objective of the PAS is to evaluate the contraceptive failure rate of Essure when NovaSure EA is performed following a successful Essure Confirmation Test and to demonstrate that the failure rate is reasonably low (see details below). Consistent with prior Essure clinical studies, a Bayesian approach will be used. The study will be considered a success if the posterior probability (PPr) that the observed failure rate at 1 year (rate_{1y}) is <2.1% is at least 95%, i.e.:

$$\text{PPr}(\text{rate}_{1y} < 0.021) > 0.95 *$$

* i.e., a Type 1 error rate of 5%

If the posterior probability that the 1-year rate is <0.021 exceeds 95%, we have shown with a high degree of confidence that the rate is at least as good as that which FDA has found acceptable for Adiana Permanent Contraceptive (PMA P070022).

Assumptions

The following assumptions were used to calculate the PAS sample size and power for the 1- and 3-year hypothesis:

- Participants in this PAS are women who have undergone the Essure procedure followed by a successful Essure Confirmation Test showing satisfactory micro-insert location and bilateral tubal occlusion on HSG OR optimal or satisfactory micro insert location on TVU;⁴⁸
- Contraceptive failure rates after Essure are very low for the PAS population as demonstrated by prior clinical studies;
- For the purposes of power calculations, the one-year pregnancy rate is modeled as $r = \text{beta}(0.5+a, 0.5+b)$, where $\text{beta}(0.5,0.5)$ is a non-informative prior and $a=0$, $b=600$,

⁴⁷ Per Amendment 4

⁴⁸ TVU confirmation testing criteria added per Amendment 6

roughly the size of the Essure Phase II and Pivotal clinical trial relying cohorts in the Essure premarket studies;

- Multiple clinical trials are simulated with the underlying pregnancy rate of r ;
- The one-sided upper Bayesian credible interval of the observed one-year failure rate amongst $n=200$ is calculated in 5000 simulated clinical trials using an underlying pregnancy rate of r ;
- Power for the 1-year hypothesis is the probability that the Upper Confidence Limit of the 1-year rate is $<2.1\%$, where 2.1% is the Upper Confidence Limit of the Adiana 1-year failure rate (Table 5: Contraceptive Failure Rates, Adiana Permanent Contraception Instructions For Use, AW-03216-001 Rev. 003);
- Power for the 3-year hypothesis is the probability that the Upper Confidence Limit of the 3-year rate is $<2.8\%$, the Upper Confidence Limit of the Adiana 3-year failure rate (Table 5: Contraceptive Failure Rates, Adiana Permanent Contraception Instructions For Use, AW-03216-001 Rev. 003).

Given the assumed underlying failure rate for a successful Essure procedure followed by a confirmatory Essure Confirmation Test, a study of $n=200$ women has an 86% chance of showing that the Upper Confidence Limit of the 1-year failure rate will be $<2.1\%$. The table below shows detailed results.

| Expected number of failures at 1 year | Probability | 2-sided upper credible interval |
|---------------------------------------|-------------|---------------------------------|
| 0 | 0.861 | 0.012 |
| 1 | 0.112 | 0.023 |
| 2 | 0.020 | 0.031 |
| 3 | 0.006 | 0.039 |
| 4 | 0.002 | 0.047 |
| 5 | 0.0004 | 0.054 |

9. Data handling and quality assurance ⁴⁹

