6.2 Efficacy

6.2.1 Primary Efficacy Analysis

The primary effectiveness endpoint of this study is the 1-year and 3-year pregnancy rates. The rates will be calculated as done in prior Essure studies, as described below.

Each woman-month of follow-up represents a “Bernoulli trial” of the Essure device. A woman contributes as many women-months as her participation in the post-approval study. Upon observing f failures (pregnancies) in w women-months, the posterior distribution of the monthly failure rate, r , is calculated as:

$$r = \text{beta}(a+f, b+w-f)$$

where a and $b = 0.5$, representing a non-informative prior distribution. The upper Bayesian credible interval of r is easily calculated from the inverse beta function. A 1-year failure rate can be calculated as:

$$1\text{-year rate} = 1 - (1 - r)^{12}$$

The 1-year rate will be calculated when all participating women have reached at least 1 year of follow-up.

As an additional related calculation, the 3-year failure rate will be determined as:

$$3\text{-year rate} = 1 - (1 - r)^{36}$$

- For example, if there are 0 failures in $200 \times 12 = 2,400$ women-months, the posterior distribution of the monthly failure rate is $\text{beta}(0.5, 0.5 + 2400)$. The upper Bayesian credible interval is (in Excel) $\text{betainv}(.975, 0.5, 0.5 + 2400) = 0.00105$. The upper 95% credible interval for the 1-year rate is $1 - (1 - 0.00105)^{12} = 0.0125$ or 1.25%. This value meets the pre-determined study success threshold of 2.1% for the 1-year rate. 2.1% refers to the Upper Confidence Limit of the Adiana 1-year failure rate and 2.8% refers to the Upper Confidence Limit of the Adiana 3-year failure rate. (from Table 5: Contraceptive Failure Rates, Adiana Permanent Contraception Instructions For Use, AW-03216-001 Rev. 003);

The analysis population is the Primary Effectiveness Cohort.

The primary objective of the PAS is to evaluate the contraceptive failure rate of Essure when NovaSure EA is performed following a successful Essure Confirmation Test and to demonstrate that the failure rate is reasonably low (see details below). Consistent with prior Essure clinical studies, a Bayesian approach will be used. The study will be considered a success if the posterior probability (PPr) that the observed failure rate at 1 year (rate1y) is $< 2.1\%$ is at least 97.5%, i.e.:

$$\text{PPr}(\text{rate1y} < 0.021) > 0.975 *$$

* i.e., a Type 1 error rate of 5%

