This equation provides the posterior probability that the one-year pregnancy rate is less than 2.1% given trial data is at least 97.5%. If the posterior probability that the 1-year rate is < 0.021 exceeds 97.5%, we have shown with a high degree of confidence that the rate is at least as good as that which FDA has found acceptable for Adiana Permanent Contraceptive (PMA P070022).

For the three-year rate, the same procedure is followed with the only exception that the threshold value is 2.8%, rather than the 2.1% specified for the one-year rate.

As a supportive analysis, the pregnancy rate will be also calculated using Kaplan-Meier method.

Assumptions

The following assumptions were used to calculate the PAS sample size and power for the 1- and 3-year hypothesis:

- Participants in this PAS are women who have undergone the Essure procedure followed by a successful Essure Confirmation Test showing satisfactory micro-insert location and bilateral tubal occlusion;
- Contraceptive failure rates after Essure are very low (no pregnancies identified in References 4 and 5 (two retrospective studies) in the clinical study protocol)) for the PAS population as demonstrated by prior clinical studies;
- For the purposes of power calculations, the one-year pregnancy rate is modeled as $r = \text{beta}(0.5+a, 0.5+b)$, where $\text{beta}(0.5,0.5)$ is a non-informative prior and $a=0$, $b=600$, roughly the size of the Essure Phase II and Pivotal clinical trial relying cohorts in the Essure premarket studies;
- Multiple clinical trials are simulated with the underlying pregnancy rate of r ;
- The one-sided upper Bayesian credible interval of the observed one-year failure rate amongst $n=200$ is calculated in 5000 simulated clinical trials using an underlying pregnancy rate of r ;
- Power for the 1-year hypothesis is the probability (based on 5000 simulated clinical trials) that the Upper Credible Interval of the 1-year rate is $<2.1\%$, where 2.1% is the Upper Confidence Limit of the Adiana 1-year failure rate (from Table 5 in the clinical study protocol: Contraceptive Failure Rates, Adiana Permanent Contraception Instructions For Use, AW-03216-001 Rev. 003);
- Power for the 3-year hypothesis is the probability that the Upper Credible Interval of the 3-year rate is $<2.8\%$, the Upper Confidence Limit of the Adiana 3-year failure rate (Table 5: Contraceptive Failure Rates, Adiana Permanent Contraception Instructions For Use, AW-03216-001 Rev. 003).

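### The protocol declares 1-year success at a posterior probability above 95%, the SAP above 97.5%; the shared 86% power and results table fit only 97.5%, and the shared 5% error is exact for neither.

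*Protocol*

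**What the plan says.** Protocol 8.6 requires a posterior probability above 0.95 that the 1-year rate is below 0.021: "If the posterior probability that the 1-year rate is <0.021 exceeds 95" per cent. SAP 6.2.1 sets the same criterion at 0.975: "If the posterior probability that the 1-year rate is < 0.021 exceeds 97.5" per cent. Each displayed rule carries the same footnote, quoted here from the SAP: "i.e., a Type 1 error rate of 5" per cent.

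The power statement is also common to both. The protocol says that 200 women give an "86% chance of showing that the Upper Confidence Limit of the 1-year failure rate will be" below 2.1%, and the SAP repeats the figure with the same table (0 failures: probability 0.861, upper limit 0.012; 1 failure: 0.112 and 0.023; and so on to 5 failures). The table's last column is headed "2-sided upper credible interval". The assumptions above it speak of "The one-sided upper Bayesian credible interval of the observed one-year failure rate amongst" 200 women. The worked example in Protocol 8.4.1 and SAP 6.2.1 takes the 0.975 quantile.

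On the 3-year rate the SAP says: "For the three-year rate, the same procedure is followed with the only exception that the threshold value is 2.8" per cent. Protocol 8.6 names a 3-year hypothesis with the 2.8% limit but gives no posterior-probability cut-off for it. SAP Section 7, whose heading covers changes to the planned analysis, lists two version dates and nothing else.

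**The concern.** These are current texts, not an amendment log set against its replacement. A success rule fixes how many pregnancies the study may observe and still succeed, so moving the cut-off from 0.95 to 0.975 should change the power and the error rate. Here neither figure moves. Either the power and table belong to one rule only, or one rule is misstated.

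At stake is the conclusion on the primary endpoint. The SAP rule is the stricter one, so any conflict runs one way: success by the protocol and failure by the SAP on the same data. If this is left open until the count is known, the choice of rule would be made after seeing the result.

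**Working it through.** **Inputs.** Threshold 2.1% at 1 year and 2.8% at 3 years; n=200; planning distribution for the true 1-year rate Beta(0.5, 600.5) (Protocol 8.6). Posterior for the monthly rate r after f pregnancies in w woman-months: Beta(0.5+f, 0.5+w−f), with 1-year rate 1−(1−r)^12 and 3-year rate 1−(1−r)^36 (Protocol 8.4.1). Design size w = 200 × 12 = 2,400.

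**1. The plan's own example.** The 0.975 quantile of Beta(0.5, 2400.5) is 0.00105, and 1−(1−0.00105)^12 = 0.0125. This reproduces.

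**2. The table's upper limits** (w = 2,400, converted to 1 year):

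| Failures | Table | 0.975 quantile | 0.95 quantile |
|---|---|---|---|
| 0 | 0.012 | 0.0125 | 0.0096 |
| 1 | 0.023 | 0.0231 | 0.0193 |
| 2 | 0.031 | 0.0316 | 0.0273 |
| 3 | 0.039 | 0.0393 | 0.0346 |
| 4 | 0.047 | 0.0465 | 0.0414 |
| 5 | 0.054 | 0.0534 | 0.0480 |

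The table matches the 0.975 quantile to within about 0.001 and does not match the 0.95 quantile. With 1 failure the limit fails 2.1% at 0.975 (0.0231) and passes at 0.95 (0.0193).

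**3. Power.** Failures among 200 women are beta-binomial(200; 0.5, 600.5): P(0) = 0.866 and P(1) = 0.108.
- 0.975 rule (0 failures allowed): 0.866. Three runs of 5,000 simulated trials gave 0.861 to 0.869, which matches the stated 86%.
- 0.95 rule (0 or 1 allowed): 0.866 + 0.108 = 0.974. The table's own rows give 0.861 + 0.112 = 0.973.

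The table's probability column does not depend on the rule. What ties 86% to 0.975 is that the 1-failure row fails.

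**4. Posterior probability that the 1-year rate is below 2.1%, w = 2,400.** 0 pregnancies: 0.996 (both rules succeed). 1: 0.963 (protocol succeeds, SAP fails). 2: 0.869 (both fail). The split at 1 pregnancy holds from 2,210 to 2,643 woman-months, which includes 220 × 12 = 2,640 (0.9749).

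**5. False success at a true 1-year rate of 2.1%, n = 200.** P(0) = 0.979^200 = 0.0143. P(0 or 1) = 0.0143 + 200 × 0.021 × 0.979^199 = 0.0759. So the 0.975 rule has 1.4% and the 0.95 rule 7.6%. With 220 women the figures are 0.9% and 5.4%.

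**6. Longer follow-up.** The analysis uses all exposure: "A woman contributes as many women-months as her participation in the post-approval study". The largest number of pregnancies still allowed then becomes:

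| Woman-months | SAP rule | Protocol rule | Posterior probability at the disputed count |
|---|---|---|---|
| 2,400 | 0 | 1 | 0.963 |
| 3,000 | 1 | 1 | none disputed |
| 5,000 | 3 | 4 | 0.961 |
| 6,900 | 5 | 6 | 0.972 |

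From 2,400 to 7,920 (220 × 36) woman-months the allowed counts differ at about 73% of sizes. That is a share of sizes, not a probability of conflict.

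**7. Three years, w = 200 × 36 = 7,200, threshold 2.8%.** 1 pregnancy gives 0.990. 2 pregnancies give 0.955, with an upper limit of 2.73% at the 0.95 quantile and 3.16% at 0.975. The split at 2 pregnancies holds from 7,018 to 8,134 woman-months.

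**The case against.** The strongest reply concerns practical weight. The 1-year analysis waits until every woman has at least 1 year, and enrolment was projected from November 2012 to December 2017 (Protocol 15). Assuming 220 women, even accrual and no dropout, exposure would by then be about 6,900 woman-months. Under the planning distribution, the probability that the count falls where the rules disagree is about 11% at 2,400 woman-months, 0 at 3,000, 0.6% at 5,000 and 0.2% at 6,900. This stands: the 0.112 belongs to the design size, or to exposure kept near it by heavy dropout. It does not carry over to 3 years, where 2 pregnancies in 7,200 woman-months have a probability of roughly 7% under the same distribution.

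Second, the protocol's own example and table use 0.975, so the outlier may be the 95% wording in 8.6, perhaps a slip between one- and two-sided intervals. That is plausible and points to the easier repair, but the displayed rule still says 0.95.

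Third, 5% can be read as the level of a two-sided 95% interval. Success is declared in one direction only, so the nominal level of the 0.975 rule is 2.5%; 5% is true there only as a ceiling.

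Fourth, the stricter SAP rule cannot create a success that the protocol would deny. That limits the harm but leaves the conflict in place.

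**Conclusion.** The concern holds. The two documents state different success thresholds for the primary endpoint and share operating characteristics that fit only one of them. The 86% power and the table belong to the 0.975 rule; the protocol's written 0.95 rule has about 97% power. At 200 × 12 woman-months the rules give opposite conclusions with exactly 1 pregnancy and agree with 0. The exact false-success probability there is 7.6% (0.95 rule) or 1.4% (0.975 rule), so the stated 5% is exact for neither.

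These figures assume 200 women with 12 complete months and, for power, the plan's own Beta(0.5, 600.5). With longer exposure the disputed count moves or vanishes and a 1-year conflict becomes improbable under that distribution. The 3-year result assumes 200 women with full follow-up. Because a stated decision rule is contradictory as written, it must be fixed.

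**What to change.** Before data release, state one threshold in Protocol 8.6 and SAP 6.2.1, apply it explicitly to the 3-year criterion in Protocol 8.6, and record the change and its reason in SAP Section 7.

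- **If 0.975 is chosen**, which already fits the worked example, the table and the 86%: change Protocol 8.6 to 0.975, replace the 5% footnotes by a one-sided nominal level of 2.5%, and give the exact error for a stated exposure (1.4% at 200 × 12).
- **If 0.95 is kept:** change the SAP to 0.95; use the 0.95 quantile in the example (1-year upper limit 0.96% instead of 1.25%) and in the table (0.010, 0.019, 0.027, 0.035, 0.041, 0.048 for 0 to 5 failures, on the woman-month basis); restate power as about 97%; and call 5% nominal, with the exact error beside it (about 7.6% at 200 × 12).

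In either case, make the one-sided wording in the assumptions and the two-sided table heading agree, and say whether the table is computed per woman or per woman-month, since the third decimal can differ.

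The cost is wording in Protocol 8.4.1 and 8.6 and SAP 6.2.1 and 7. No data or subjects are added; only the stated power or error level changes.
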